17.2.1 Study Power

Utilizing a minimum effectiveness rate of 66% (OPC), an expected success rate of approximately 78% for Minitouch, and a one-sided alpha of 0.025, the study sample size required to obtain at least 80% power is 114 Patients. Assuming a dropout rate of approximately 10% at 12 months, the required enrolled sample size is determined to be 126 Patients.

The 78% investigational device success rate is derived from other GEA studies recently conducted and published. For sample size calculation, Minerva utilized an expected success rate of 78% (Laberge et al. J Minim Invasive Gynecol 2015;7:1169-77) and Aegea utilized an expected success rate of 76% (Levie MD, Chudnoff SG. J Minim Invasive Gynecol 2018; S1553-4650).

Multiple scenarios were used to calculate the sample size. Statistical Analysis Software (SAS) POWER procedure Z test for binomial proportion was utilized with the following fixed scenario elements: normal approximation method, 66% null proportion, 0.025 one-sided alpha, 80% nominal power, and null variance estimate.

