17.2 Analysis of Primary Efficacy Endpoint at 12-month

The primary efficacy endpoint is binary (success/failure). Success is defined as PBLAC score of \leq 75 at the 12-month follow-up assessment without incidence of additional interventions or treatments for bleeding prior to the 12-month follow-up visit. The proposed study's primary hypothesis is:

Null Hypothesis (H₀) = $p_{minitouch} \le OPC$

Alternate Hypothesis (H₁) = p_{minitouch} > OPC

where p_{minitouch} is the Minitouch Endometrial Ablation System success rate and OPC is 66% which is the FDA identified objective performance criterion (OPC) for global endometrial ablation (GEA) devices.

The exact binomial test will be conducted to compare the investigational device success rate to OPC minimum success rate for effectiveness. To achieve study success the measured success rate should exceed the 66% OPC.

ITT with imputation will be utilized to test the primary hypothesis, such that all missing data are failures for the primary endpoint. The following imputation techniques will be conducted for sensitivity analysis:

- Multiple Imputation (MI) using fully conditional specification (FCS) method, in which logistic regression is used to predict whether the missing value is likely to be a success or failure. The number of imputations will depend on the fraction of missing information.
- Tipping point, in which the numbers of successes or failures amongst missing data necessary to meet the primary endpoint hypothesis are determined.

Fisher-Freeman-Halton test will be conducted to compare the success rates between investigational sites. Results will also be stratified and compared across relevant baseline characteristics including demographics.

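### Section 17.2.1 takes its power of at least 80% at 114 patients from a Z-test approximation; the exact binomial test planned in Section 17.2 gives 78.3% at that size (minor sizing-method mismatch)

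*Combined protocol and SAP*

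**What the plan says.** Section 17.2.1 (Study Power) gives these inputs: "Utilizing a minimum effectiveness rate of 66% (OPC"), "an expected success rate of approximately 78% for Minitouch" and "a one-sided alpha of 0.025". From them it concludes that "the study sample size required to obtain at least 80% power is 114 Patients", and it raises this to 126 enrolled for a dropout of about 10% at 12 months.

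The same section discloses its method: "POWER procedure Z test for binomial proportion was utilized with the following fixed scenario elements: normal approximation method", with "80% nominal power, and null variance estimate".

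Section 17.2 (Analysis of Primary Efficacy Endpoint at 12-month) plans a different test: "The exact binomial test will be conducted to compare the investigational device success rate to OPC minimum success rate for effectiveness". It applies that test to the ITT cohort with every missing outcome counted as a failure. Section 17.1.1 defines ITT as all eligible patients in whom the procedure is initiated.

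Neither section gives the power of the exact test, or the number of successes needed to reject the null hypothesis.

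**The concern.** The size was worked out for one test and the data will be judged by another. The exact test counts whole successes, so it usually cannot use its full 2.5%. The normal-approximation power formula treats the cut-off as continuous and ignores this. A sample size that only just reaches 80% on the smooth formula can therefore fall below 80% under the planned test.

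What is at stake is whether a stated floor is true. The effectiveness conclusion of this single-arm study rests on one binomial count against a fixed 66%. Any reader can recompute the power of that test, and will find that it does not match Section 17.2.1.

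**Working it through.** **Inputs.** From Section 17.2.1: p0 = 0.66, p1 = 0.78, one-sided alpha = 0.025 (z = 1.960), target power 80% (z = 0.8416), n = 114, enrolment 126, dropout about 10%. From Section 17.2: exact binomial test, ITT, missing = failure.

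**Step 1: reproduce 114.** One-sample Z test, with the null variance for the critical value and the alternative variance for the power:

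n = [(1.960 × √(0.66 × 0.34) + 0.8416 × √(0.78 × 0.22)) / (0.78 − 0.66)]²

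= [(1.960 × 0.4737 + 0.8416 × 0.4142) / 0.12]² = 113.26, rounded up to 114.

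Power from the same formula is Φ[(√n × 0.12 − 1.960 × 0.4737) / 0.4142], which is 79.9% at n = 113 and 80.3% at n = 114. The plan's figure reproduces exactly.

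**Step 2: the exact test at 114.** Find the smallest r with P(X ≥ r | 114, 0.66) ≤ 0.025.

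| r | P(X ≥ r) at 66% | P(X ≥ r) at 78% |
|---|---|---|
| 85 | 0.0314 (too large) | 0.841 |
| 86 | 0.0193 | 0.783 |

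The cut-off is 86 of 114, the true one-sided size is 1.9%, and the power is 78.3%. The shortfall against the stated floor is 80.0 − 78.3 = 1.7 points. Every one of the 114 is assumed to have an outcome, so dropout plays no part in it.

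**Step 3: would the Z test itself reach 80% at 114?** It rejects when the count exceeds 114 × 0.66 + 1.960 × √(114 × 0.66 × 0.34) = 75.24 + 9.91 = 85.15, that is, at 86 or more. This is the same rejection region as the exact test, so the true power of the Z test at 114 is also 78.3%. The 80.3% belongs to the smooth formula only.

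**Step 4: the denominator that will be tested.** At n = 126, 93 successes give a tail probability of 0.0374 at 66% and 94 give 0.0239. The cut-off is 94 of 126, with one-sided size 2.4%. Power at 78% is 84.8%, provided that 78% is the ITT success rate with missing patients already counted as failures.

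**Step 5: sensitivity to the 78%.** The plan calls this rate approximate.

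| True rate | Exact power, n = 114 (cut-off 86) | Exact power, n = 126 (cut-off 94) |
|---|---|---|
| 77.5% | 74.3% | 81.3% |
| 78.0% | 78.3% | 84.8% |
| 78.25% | 80.2% | 86.4% |
| 78.5% | 82.0% | 87.8% |

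**Step 6: sizes other than 114.** Exact power first reaches 80% at n = 116 (81.5%), falls below it at 118 (78.7%) and 122 (79.0%), and stays at or above 80% from 123. With about 10% dropout, 116 would need 116 / 0.9 = 128.9 enrolled and 123 would need 123 / 0.9 = 136.7. Neither fits 126.

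**The case against.** The strongest reply is that nothing was miscalculated. Section 17.2.1 names its procedure, approximation and variance choice, calls the power nominal, and 114 follows exactly from them. That stands: this is a mismatch between sizing method and planned test, not an arithmetic slip. Disclosure explains the figure but does not make the floor true, since the Z test also has 78.3% true power at 114 (Step 3).

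A second reply is that 114 is not the size at which the primary test will be run. Patients who drop out stay in the ITT denominator as failures, so at planned enrolment it is 126. This also stands, and it limits the point to a statement about an intermediate number.

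A third is that the gap is smaller than the precision of the input: a true rate of 78.25% removes it. That is right, and it is a reason to grade the point as minor.

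A reader might go further and infer that the trial is underpowered, or that more patients are needed. The mismatch does not support that. If 78% is the ITT rate, exact power at 126 is 84.8%. If 78% applies to completers only and 10% are missing, the ITT rate is 0.9 × 78% = 70.2% and exact power at 126 is about 16%. That would be a far larger problem, but it comes from how dropouts are counted and not from the choice between the exact test and the Z test. The documents do not say which reading of 78% is meant.

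**Conclusion.** The point holds, as a minor one. Under the test named in Section 17.2, 114 analysed patients give 78.3% power at a true rate of 78%, against a stated minimum of 80%. The cause is a disclosed normal approximation that ignores the discreteness of the count. The result assumes 66% against exactly 78%, one-sided 0.025, and 114 complete outcomes.

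It does not show that enrolment of 126 is too small. At 126 the exact test has 84.8% power, on the condition that 78% already counts missing patients as failures.

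**What to change.** Revise one paragraph in Section 17.2.1, and carry the same figures into any separate SAP:

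- Keep enrolment at 126.
- State that 114 came from the Z-test approximation (nominal power 80.3%) and that exact binomial power at 114 is 78.3% (cut-off 86, one-sided size 1.9%).
- Report the exact test at the planned ITT denominator: at least 94 successes of 126, one-sided size 2.4%, power 84.8% at 78%.
- Say that the 84.8% treats 78% as the ITT success rate with missing outcomes already counted as failures, or give the power under whichever meaning of 78% was intended.
- State that the cut-off will be recomputed by the same exact rule if the final ITT count is not 126.

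Do not put 116 or 123 in place of 114 while keeping 126: the room left for dropout would shrink to 10/126 = 7.9% or 3/126 = 2.4%, against the stated figure of about 10%.

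The cost is a wording change and a slightly less favourable figure at 114. No extra patients are needed on this ground, and the test and alpha stay as they are.

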17.1.1 Intent-to-Treat (ITT) Cohort

All patients who are enrolled in the study (enrollment defined as patients who met all study eligibility criteria and in whom the procedure is initiated) are included in the Intent-to-Treat (ITT) cohort.

The ITT cohort will be used for the following analyses (as defined in Section 9.1 & 9.2):

- Primary safety and effectiveness analyses at 12-month follow-up visits.
- Safety & effectiveness analyses at 24, and 36-month follow-up visits.

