17.1.2 Per Protocol (PP) Cohort

This cohort consists of all ITT Patients who are considered treatable patients, completed ablation therapy and attended 12-month follow-up visit.

The PP cohort will be used for the following analyses:

- Safety and efficacy outcome measures at 12, 24, and 36-month follow-up visits
- Secondary Analyses to assess amenorrhea rates, improvement of quality of life, evaluate patient and user (investigator) satisfaction.
- Subgroup Analyses
- Exploratory Analyses

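### The dropout allowance that takes 114 patients to 126 does not match a primary analysis that counts dropouts as failures, and the basis of the 78% is not stated

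*Combined protocol and SAP*

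**What the plan says.** Section 17.2.1 (Study Power) takes a 66% null rate, an expected rate of about 78% and a one-sided alpha of 0.025, and concludes that "the study sample size required to obtain at least 80% power is 114 Patients". The method is a one-sample Z test with "normal approximation method, 66% null proportion, 0.025 one-sided alpha, 80% nominal power, and null variance estimate". It then adds: "Assuming a dropout rate of approximately 10% at 12 months, the required enrolled sample size is determined to be 126 Patients". On the source of the expected rate it says: "The 78% investigational device success rate is derived from other GEA studies recently conducted and published", and cites planning rates of 78% and 76% from two device trials. It does not say how those rates treat missing outcomes.

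Section 17.2 (Analysis of Primary Efficacy Endpoint) specifies a different test from the one used for sizing: "The exact binomial test will be conducted to compare the investigational device success rate to OPC minimum success rate for effectiveness". On missing data it says: "ITT with imputation will be utilized to test the primary hypothesis, such that all missing data are failures for the primary endpoint".

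Under Section 17.1.1, eligible patients "in whom the procedure is initiated) are included in the Intent-to-Treat (ITT) cohort", and that cohort is primary. Section 11.8 counts a patient terminated before the 12-month visit as a treatment failure, and Section 11.8.1 says withdrawn or lost patients are not replaced. Only the per-protocol cohort of Section 17.1.2 is limited to women who "completed ablation therapy and attended 12-month follow-up visit".

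**The concern.** Enrolling extra patients for dropout assumes that dropouts vanish from the analysis and that about 114 evaluable women remain, succeeding at the planned 78%. In the primary analysis nobody vanishes. All 126 stay in the denominator, and each missing outcome is scored as a failure. Dropout therefore acts on the success rate, the quantity to which power is most sensitive here, and a 10% increase in N does little to offset that.

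Section 17.2.1 reads as if 10% dropout had been dealt with. If the 78% already counts missing as failure, the allowance is not what provides the power. If the 78% is a rate among women with data, the allowance does not protect the power. Either way, a reader cannot learn from this section what power the planned primary test has at the plan's own dropout rate. What is at stake is a false-negative pivotal trial, not a false-positive one.

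**Working it through.** **Inputs.** Null rate 0.66, expected rate 0.78, one-sided alpha 0.025, 80% power, 114, about 10% dropout and 126 (Section 17.2.1). Exact binomial test in ITT with missing as failure (Sections 17.1.1 and 17.2). Success requires the lower 95% confidence bound to exceed 66% (Section 9.1), which corresponds to a one-sided exact test at 0.025.

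**1. The plan's own figures.** With null variance,

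n = [(1.96·√(0.66·0.34) + 0.8416·√(0.78·0.22)) / 0.12]² = [(0.9285 + 0.3486) / 0.12]² = 113.26, rounded up to 114. Z power at 114 is 80.3%.

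Dropout step: 113.26/0.90 = 125.8 and 114 × 1.10 = 125.4, both rounding up to 126 (114/0.90 = 126.7 would give 127). Both stated figures reproduce.

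**2. The planned exact test.** The critical count is the smallest c with P(X ≥ c | N, 0.66) ≤ 0.025. Power is P(X ≥ c | N, p).

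| N | Successes needed | Exact size | Power at p = 0.78 |
|---|---|---|---|
| 114 | 86 | 0.0193 (85 would give 0.0314) | 78.3% |
| 116 | 87 | 0.0236 | 81.5% |
| 122 | 92 | 0.0161 | 79.0% |
| 126 | 94 (74.6%) | 0.0239 (93 would give 0.0374) | 84.8% |

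Exact power first reaches 80% at N = 116, dips below at some sizes, and stays at or above 80% from N = 123 (checked to 199). So 114 falls slightly short under the planned test and 126 does not. At N = 126, 80% power needs an ITT success rate of about 77.3%.

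**3. Reading A: the 78% already counts missing as failure.** The tested rate is 0.78 and exact power at 126 is 84.8%, with no separate dropout allowance. For reference, power is 68.6% at an ITT rate of 76% (the other planning rate in Section 17.2.1) and 64.8% at 75.6% (the pooled device rate in Section 6).

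**4. Reading B: the 78% is the rate among women with 12-month data.** With a missing fraction d, the tested rate is 0.78 × (1 − d).

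| Missing | Tested ITT rate | Exact power, N = 126 |
|---|---|---|
| 0% | 0.780 | 84.8% |
| 2% | 0.7644 | 72.7% |
| 5% | 0.741 | 49.6% |
| 10% | 0.702 | 16.3% |

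At 10% missing, 80% power needs a completer rate of about 0.7732/0.90 = 85.9%.

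**5. Sensitivity to who drops out.** Suppose 78% is the rate that complete data on everyone would show, and a share s of the 10% who drop out would have succeeded. The tested rate is then 0.78 − 0.10·s. The values of s are assumptions; the documents give none.

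| s | Tested rate | Exact power, N = 126 |
|---|---|---|
| 0% | 0.780 | 84.8% |
| 25% | 0.755 | 63.8% |
| 50% | 0.730 | 38.6% |
| 78% | 0.702 | 16.3% |

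**The case against.** The best defence is that Reading A is the natural one. Section 17.2.1 sets the 78% directly against the 66% OPC. Section 6 says the trials behind that OPC scored missing 12-month diaries as failures, and Section 17.2 tests Minitouch on the same basis. The pooled 75.6% from those trials lies close to the 76% and 78% planning rates. On that view the 78% is already an ITT rate, power at 126 is 84.8%, and the 12 extra patients are margin. This supports A but does not establish it: Section 6 describes the OPC trials, and Section 17.2.1 does not tie the 78% to them. Adding patients for dropout fits a rate that applies to women with data, which points the other way, though it is not proof either.

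It is also fair that the 16.3% rests on three conditions together: a completer rate, the full 10% missing, and dropouts no less successful than completers. It is a lower end, not a forecast. Even so, 2% missing under Reading B already takes power below 80%.

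Finally, the allowance has one legitimate use. It keeps about 126 × 0.90 = 113.4 women for the per-protocol analysis. That stands, but it does not justify the power of the primary test.

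**Conclusion.** The concern holds. The arithmetic behind 114 and 126 is sound; the fault is that the dropout step assumes an analysis the plan does not use for its primary test, and that the 78% is undefined. Exact power at 126 is 84.8% if the 78% counts missing as failure. If it is a completer rate, power runs from 84.8% with nothing missing down to 16.3% at 10% missing, the latter assuming dropout unrelated to outcome.

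These figures use the confidence-bound success rule of Section 9.1, not the looser sentence in Section 17.2 that the measured rate should exceed 66%. The exact size of 0.0239 is unaffected by dropout. The documents do not settle which reading is right, so this is not a finding that the trial is underpowered. It should be fixed, because the stated power cannot be traced to the planned test.

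**What to change.** Keep N = 126, the exact binomial test and missing-as-failure. In Section 17.2.1:

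1. State whether the 78% counts missing outcomes as failures or is a rate among women with 12-month data.
2. Stop giving the dropout inflation as the reason for 126 in the primary test, and present 126 as the fixed ITT size. The expected loss can still be mentioned for the per-protocol cohort.
3. Replace the Z-approximation power with exact power at 126: 94 or more successes needed, and 80% power at an ITT rate of about 77.3%.
4. If the 78% counts missing as failure, state 84.8% and make no separate dropout allowance. If it is a completer rate, give power at 0%, 2%, 5% and 10% missing (84.8%, 72.7%, 49.6%, 16.3%), label the last as the low end, and note that about 85.9% among completers is needed for 80% power at 10% missing.

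The cost is protocol and SAP wording. No patients are added, and the test, success rule and missing-data rule do not change. The stated power may look less favourable.

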17.3 Predictive Analysis 12, 24, and 36-month Efficacy Outcome

Univariate analyses will be conducted using analysis of covariance (ANCOVA) to evaluate the effect of demographics, gynecologic history, procedure-related characteristics and diagnosis of COVID-19 or COVID-19 vaccination status on PBLAC score post procedure, while controlling for baseline PBLAC scores.

17.4 Analysis of Primary Safety Endpoint at 12-month

The primary safety endpoint is the rate of device or procedure-related serious adverse events. It will be evaluated 12 months post-procedure.

17.5 Analysis of All Safety Outcome

All safety events reported in the study will be tabulated. The study's safety analysis focuses on specific device- or procedure-related safety events listed in Section 13. Intra-operative and post-operative serious adverse event (SAE) and overall rates of AEs (number and percentage with 95% confidence interval) will be reported.

The need for medical or surgical intervention to treat abnormal bleeding following the ablation procedure will also be reported.

17.6 Analysis of Secondary Endpoints

No hypothesis will be tested with regards to secondary endpoints. Secondary endpoints will be reported using descriptive statistics along with sample size. Measures of central tendency (mean, median, and mode) and of variation (range and standard deviation) for continuous variables. Measures of frequency (count and proportions) for categorical variables.

17.7 Subgroup Analyses

The following subgroup analyses will be performed for both treatment success (reduction of menstrual blood loss) and amenorrhea rates for the following timepoints during study follow-up: 12, 24, and 36-months post procedure.

- Age (<40 years vs. >40 years)
- Active bleeding at the time of the operative visit (Yes vs. No)

- Transverse or low segment C-section (Yes vs. No)
- Anesthesia regimen (None vs. Sedation vs. Local Anesthesia vs. General Anesthesia vs. Multiple)
- Use environment (Office vs. Non-office)
- Uterine sound depth (6-9.0cm vs. 9.1-12cm and 6-8.0cm vs. 8.1-10cm vs. 10.1-12cm)
- Presence of anemia at Baseline defined as hemoglobin < 12 g/dL (Yes vs. No)
- Presence of fibroids at Baseline (Yes vs. No)
- Presence of ovarian cysts at Baseline (Yes vs. No)
- Presence of any intrauterine pathology at baseline (Yes vs. No)
- Contraceptive use (hormonal method vs. non-hormonal method)
- COVID-19 Status (diagnosed with COVID-19 vs. did not have COVID-19)
- COVID-19 Vaccination Status (vaccinated vs. not vaccinated)

The study is not powered for these subgroups, and therefore, there will be no hypothesis testing for the primary endpoints within these groups. These analyses will be done using the PP population.

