5 PROTOCOL SYNOPSIS

| Title | Minitouch Endometrial Ablation System Treatment for Menorrhagia: An Evaluation of Safety & Effectiveness | | |
|---|---|--|--|
| Short Title | EASE Clinical Trial | | |
| IDE No. | G180282 | | |
| ClinicalTrials.gov Identifier | NCT04267562 | | |
| Protocol No. & Revision | TD18036 v5.0 | | |
| Version Date | 14Dec2021 | | |
| Study Device | Minitouch Endometrial Ablation System ("Minitouch System") | | |
| Proposed Indications for Use | The Minitouch Endometrial Ablation System is intended for ablation of the endometrial lining of the uterus for the treatment of menorrhagia (heavy menstrual bleeding) due to benign causes in premenopausal women for whom childbearing is complete | | |
| Study Design This is a prospective, multi-center, open-label, single-arm, clinical investigation study Design evaluate the Minitouch Endometrial Ablation System in premenopausal women menorrhagia menorrhagia | | | |
| Study Objective | To evaluate the safety and effectiveness of the Minitouch System | | |
| Study Duration | At least 37 months, including an estimated one month of pre-enrollment assessment and 36 months post-treatment follow up | | |
| Planned Number of Sites | Approximately 10 sites from the United States only | | |
| Planned Enrollment | Up to 126 premenopausal women with menorrhagia | | |
| Primary Effectiveness Endpoint | Percent of patients demonstrating reduction of menstrual flow as evidenced by a Pictorial Blood Loss Assessment Chart (PBLAC) score of \leq 75 at the 12-month post procedure time point | | |
| Study Success | To achieve study success, 12-month success rate should exceed the 66% Objective Performance Criterion (OPC) developed by the FDA, outlined in correspondence of Oct 29, 2015 ⁽¹⁾ | | |
| Primary Safety Measure | Reported rate of device and procedure-related serious adverse events at 12-months post-procedure as adjudicated by the CEC | | |

CONFIDENTIAL & PROPRIETARY

Page 14 of 65

Page 15 of 65

| Secondary effectiveness outcome measures include the following: | | | | |
|---|--|--|--|--|
| | DRIAC: at 6 and 12 months | | | |
| | Monstrual Status at 6 and 12 months categorized by: | | | |
| | Interstrual Status at 6 and 12 months categorized by: | | | |
| | • Amenorrhea: PBLAC score U | | | |
| | ○ Light Bleeding: PBLAC score 0 ≤ 35.0 | | | |
| | • Normal Bleeding: PBLAC score 35.1 to 75.0 | | | |
| | • Eumenorrhea: PBLAC score 75.1 to 99.9 | | | |
| | Menorrhagia: PBLAC score >100 | | | |

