9.3 Secondary Outcome Measures

Secondary effectiveness and safety outcome measures will be assessed at the timepoints described below.

The secondary safety outcome measure at 24 and 36 months will include all device or procedure-related adverse device effects, SAEs and unanticipated adverse device effects (UADE) are defined in **Section 14 Adverse Event Reporting**.

Any medical surgical intervention to treat abnormal bleeding following the ablation procedure is considered a treatment failure. If menstrual status is assessed as "High/Heavy" by the investigator at the 24 or 36-month follow-up, the patient will be considered a treatment failure.

Secondary effectiveness outcome measures will include the following:

Patient Global Evaluation (PGE): at 6, 12, 24 and 36 months

- Patient satisfaction with treatment
- Menstrual status
- Recommend to friends

Investigator Global Evaluation (IGE): at 6, 12, 24 and 36 months

- Investigator satisfaction with treatment
- Menstrual status

Quality of Life Measures: at 6, 12, 24 and 36 months

- Improvement of quality of life as measured by:
 - Menorrhagia Impact Questionnaire (MIQ)
 - o Dysmenorrhea-related Numerical Rating Scale (NRS) pain score

Procedure:

•

- Endometrial ablation procedure-related Numerical Rating Scale (NRS) pain score
 - The following parameters will also be collected:
 - Total procedure time
 - Total treatment time (total energy delivery time)

Page 24 of 65

CONFIDENTIAL & PROPRIETARY

- Total procedure energy in joules
- Anesthesia regimen
- Procedure-related pain at pre-procedure (baseline), discharge and 24-hours postprocedure
- Need for cervical dilation

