On a scale of 0 to 10, with 0 being no pain and 10 being the worst pain possible, please mark the appropriate box that best describes your menstrual pain.

| □0 | □1 | □ 2 | □ 3 | □ 4 | □ 5 | □ 6 | □ 7 | □ 8 | □ 9 | □ 10 |
|------|----|-----|-----|-----|---------|-----|-----|-----|-----|----------|
| No | | | | | Moderat | e | | | | Worst |
| Pain | | | | | Pain | | | | | Pain |
| | | | | | | | | | | Possible |

Numerical Rating Scale (NRS) for Procedure-related Pain

On a scale of 0 to 10, with 0 being no pain and 10 being the worst pain possible, please rate your **procedure-related pain** by marking the appropriate box that best describes your pain NOW.

| □0 | □1 | □ 2 | □ 3 | □ 4 | □ 5 | □ 6 | □ 7 | □ 8 | □ 9 | □ 10 |
|------|----|-----|-----|-----|---------|-----|-----|-----|-----|----------|
| No | | | | | Moderat | e | | | | Worst |
| Pain | | | | | Pain | | | | | Pain |
| | | | | | | | | | | Possible |

CONFIDENTIAL & PROPRIETARY

| ATTA GLOE | ACHMENT D: SAMPLE RAT BAL EVALUATION OF SATIS | 'ING SFAC | SCALE FOR PATIEI | NT A TUD | ND USER (INVESTIGATOR) Y TREATMENT | | | | |
|--------------|--|---|------------------------|-------------|---------------------------------------|--|--|--|--|
| Patient Glo | bal Evaluation (PGE) | | | | | | | | |
| Are you | u satisfied with the treatment yo | ou re | ceived for menorrhagi | ia? | | | | | |
| | Very Satisfied | | Satisfied | | | | | | |
| | Not Sure | | Dissatisfied | | Very Dissatisfied | | | | |
| How w | ould you describe your menstru | ial sta | atus? | | | | | | |
| | No Bleeding (Amenorrhea) | | | | | | | | |
| | Spotting | | | | | | | | |
| | Light Bleeding (Hypomenorrh | ea) | | | | | | | |
| | Medium or Normal Bleeding | Medium or Normal Bleeding (Eumenorrhea) | | | | | | | |
| | High or Heavy Bleeding (Men | orrha | agia) | | | | | | |
| Would | you recommend this procedure | e to y | our friends? | | | | | | |
| | Yes | | | | | | | | |
| | No | | | | | | | | |
| Investigato | r Global Evaluation (IGE) | | | | | | | | |
| Are you | u satisfied with the treatment th | nis pa | tient received for mer | norrh | agia? | | | | |
| | Very Satisfied | | Satisfied | | | | | | |
| | Not Sure | | Dissatisfied | | Very Dissatisfied | | | | |
| How w | ould you describe the patient's | mens | strual status? | | | | | | |
| | No Bleeding (Amenorrhea) | | | | | | | | |
| | Spotting | | | | | | | | |
| | Light Bleeding (Hypomenorrh | ea) | | | | | | | |

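### Amenorrhea is scored on bleeding alone, so a woman who needed a further intervention for bleeding can be a treatment failure in one table and amenorrheic in the next

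*Combined protocol and SAP*

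**What the plan says.** **Treatment success.** Section 17.2 (like 9.1) requires a 12-month PBLAC score of 75 or less "without incidence of additional interventions or treatments for bleeding prior to the 12-month follow-up visit". Section 9.3 adds, without a time limit: "Any medical surgical intervention to treat abnormal bleeding following the ablation procedure is considered a treatment failure". It also makes a woman a failure if the investigator rates her bleeding as heavy at 24 or 36 months.

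**Amenorrhea and menstrual status.** The synopsis sets menstrual status at 6 and 12 months by PBLAC score bands, with amenorrhea at a score of 0. The Patient and Investigator Global Evaluations (PGE, IGE) give a second measure at 6, 12, 24 and 36 months. Their best category in Attachment D is "No Bleeding (Amenorrhea"). Neither measure refers to earlier interventions.

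**Analysis.** Section 17.1.2 assigns to the PP cohort "Secondary Analyses to assess amenorrhea rates, improvement of quality of life" and satisfaction. PP membership needs a treatable patient, completed ablation and attendance at month 12. Section 17.7 lists amenorrhea beside treatment success, also in PP: its subgroup analyses cover "both treatment success (reduction of menstrual blood loss) and amenorrhea rates for the following timepoints", which are 12, 24 and 36 months. Section 17.6 gives descriptive statistics only. Section 17.5 reports the need for interventions as a separate item.

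**The concern.** The plan recognises an intervention for bleeding as failure of the ablation, but it applies that only to success and failure. Menstrual status is left to the bleeding record, and an intervention can abolish bleeding. Section 6 itself describes hysterectomy as ending menstruation altogether. Read literally, removal of the uterus because the ablation did not work would place a woman in the best bleeding category.

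At stake is the meaning of the amenorrhea rate, overall and by subgroup. It would mix women whose bleeding stopped after the ablation with women whose bleeding stopped because something else was done. The number in the second group can only rise with time, so the 24- and 36-month figures are the more exposed. The same woman could appear with opposite classifications in two tables of one report.

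**Working it through.** **1. Does any rule carry failure over to amenorrhea?**

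| Place | Rule | Effect on amenorrhea |
|---|---|---|
| 9.1, 17.2 | Intervention before the 12-month visit rules out success | None stated |
| 9.3 | Any intervention for bleeding is treatment failure | None stated |
| 9.3 | Heavy bleeding at 24 or 36 months is failure | Runs from status to failure only |
| Synopsis | PBLAC of 0 is amenorrhea | Score only |
| Attachment D | No-bleeding category | Reported bleeding only |
| 17.1.2 | PP membership | Intervention is not a reason for exclusion |
| 17.5 | Interventions tabulated | Separate count; rate unchanged |

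No row scores a woman as not amenorrheic because she is a treatment failure.

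**2. Two timings**

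- *Intervention before the 12-month visit.* She is a primary failure. If she attends month 12 she can be in PP. She is amenorrheic by PBLAC if she returns a diary scoring 0, and by PGE/IGE if no bleeding is recorded.
- *Intervention after the 12-month visit.* Her primary result and PP membership are already fixed. She is a treatment failure under 9.3. Table 23-1 schedules diary collection only through month 12, so amenorrhea at 24 and 36 months appears to rest on PGE/IGE, where she can be recorded as having no bleeding.

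**3. Denominator**

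The plan gives no amenorrhea figure to reproduce. Its sample size serves only to set a plausible PP size. With the inputs of 17.2.1 (66% versus 78%, one-sided 0.025, 80% power, null variance):

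n = [(1.960 × √(0.66 × 0.34) + 0.842 × √(0.78 × 0.22)) / 0.12]² = 113.26, rounded up to 114, as stated.

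Enrolment of 126 less the assumed 10% dropout is 113.4. I therefore take PP as about 114. This is an assumption, since PP also requires a treatable patient and a completed ablation.

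**4. Size**

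Let m be the number of PP women with an earlier intervention who are recorded as not bleeding. The overstatement, against scoring them as not amenorrheic, is m / N. The documents do not give m; 1 to 11 is an assumed range.

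| m | m / 114 |
|---|---|
| 1 | 0.9 points |
| 3 | 2.6 points |
| 6 | 5.3 points |
| 11 | 9.6 points |

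The result is not sensitive to N: if all 126 were in PP, one woman would add 1/126 = 0.8 points.

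**5. Example with m = 6**

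Assume 45% amenorrhea among the 108 women without an intervention: 0.45 × 108 = 48.6, taken as 49.

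- Bleeding alone: (49 + 6) / 114 = 48.2%
- Scored as not amenorrheic: 49 / 114 = 43.0%
- Dropped from the denominator: 49 / 108 = 45.4%

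At assumed rates of 30% and 60% the first two figures are 33.3% versus 28.1% and 62.3% versus 57.0%. The gap is 5.3 points each time.

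**The case against.** **Section 9.3 already deals with interventions within the secondary outcomes.** This is the strongest reply. It does classify the woman, but as a treatment failure; it does not say how her menstrual status is scored, and 17.7 keeps the two outcomes apart.

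**A separate SAP may hold the rule.** Section 17 says the SAP will describe data sets and methods, and no separate SAP text is in the file. A derivation there would close the point. The protocol says it outlines the key elements, and this one is absent.

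**Many such women would not reach the table.** This stands in part. Section 11.8.1 allows discontinuation after a change of treatment, women agree at entry not to start other medical interventions for bleeding, and one who misses month 12 is outside PP. None of this guarantees removal, but the claim must be that she can count as amenorrheic, not that she will. Hormones or a repeat ablation also need not bring the score to 0.

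**Reporting status as observed, with interventions listed alongside, is usable.** It is, if the amenorrhea table itself shows the number. A count in a safety table does not tell the reader how many of the amenorrheic women it covers.

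**Stronger readings the documents do not support.** A reader might infer that every such woman is a primary failure; that holds only for intervention before the 12-month visit. A reader might also extend the point to quality of life and satisfaction. MIQ items 1 to 4 ask about the most recent period, which after a hysterectomy may be the heavy one before surgery, and the PGE asks about satisfaction with the study treatment. The argument fits the dysmenorrhea scale better, but separate summaries for these measures are a matter of preference.

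**Conclusion.** The point holds for amenorrhea and menstrual status. Applied as written, the definitions allow a treatment failure to be reported as amenorrheic at 12, 24 and 36 months, and for hysterectomy the direction of the error is clear.

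The tabulated points in the working are upper bounds, not estimates: they suppose that every one of the m women stays in PP and is recorded as having no bleeding, and both m and the PP size are assumed. With one or two such women the effect is small; with several it could change how the rate reads.

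It would be wrong to infer any threat to the primary result. The primary endpoint has its own intervention rule, and the sample size is unaffected. The consequence is confined to descriptive secondary and subgroup results, for which no hypothesis is tested. It should be settled before the tables are produced.

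**What to change.** In the synopsis, 9.3, 17.6 and 17.7, state that from the date of any intervention for bleeding a woman is scored as a treatment failure and as not amenorrheic in every later amenorrhea and menstrual-status table, that she stays in the denominator, and that each table shows the number of such women. Keeping her in the denominator matters, because dropping her would leave part of the overstatement in place, as the example shows.

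This is a scoring rule only and changes nothing in patient care. It needs one derived flag. Table 23-1 already records medications and treatments at every follow-up visit through month 36, so no new data are required. The cost is the wording change and a slightly lower reported amenorrhea rate.
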